5 RESEARCH QUESTION/AIM(S)

Study aim

To determine the feasibility and acceptability of SNMES as an exercise therapy, for preventing muscle weakness, improving walking, fatigue and quality of life in people with MS to inform a future definitive trial of clinical and cost effectiveness.

5.1 OBJECTIVES

Study objectives:

- Estimate screening, recruitment and attrition rates.
- Determine the acceptability of the intervention and key aspects of study design including intervention adherence rates, drawing on the Theoretical Framework of Acceptability (TFA).⁴³
- Explore, via qualitative interviews, individuals' experiences of study participation (and where possible, reasons for non-participation) to gather feedback about the intervention, outcome measures and study procedures.
- Inform primary outcome measure selection for a future trial.
- Determine sample size for a future trial, informed by parameter estimates of outcomes.
- Evaluate the acceptability and feasibility of health economics measures, including selection and ordering of questionnaires.

5.2 OUTCOME

To determine if a future definitive trial exploring the effectiveness and cost effectiveness of SNMES is feasible and warranted, and identify any requirements for improving recruitment, retention and delivery of the intervention.

6 STUDY SETTING

Multiple sclerosis services based at the Walton Centre, Liverpool and the Royal Wolverhampton NHS Trust. Activities across both sites will be the same. SNMES will be used at home with baseline and follow up appointments at the hospital sites.

7 SAMPLE AND RECRUITMENT PARTICIPANT ENTRY

7.1 ELIGIBILITY CRITERIA

7.1.1 For people with MS involved in the randomised controlled trial

7.1.1.1 Inclusion Criteria

- Adults with primary progressive, secondary progressive or relapsing remitting MS.
- Expanded disability status scale score ≥ 4.0 and ≤ 6.5 .
 - 4= Significant disability, self-sufficient and up and about some 12 hours a day.
Able to walk without aid or rest for 500m.
 - 6.5= Requires two walking aids to walk about 20m without resting)

7.1.2 Exclusion Criteria

- Clinically isolated syndrome.
- People with MS in an active relapse or <8 -weeks since a relapse.
- Lower-limb peripheral nerve injury.
- Fixed lower-limb contractures.
- Contraindications to SNMES.
 - Pregnancy
 - Uncontrolled Epilepsy
 - Any of the following in the lower limbs
 - Peripheral nerve injury
 - Unstable fractures or orthopaedic condition affecting the lower limb
 - Cancer (malignancy) in the areas of the electrode placement
 - Skin infection / devitalised skin at the electrode placement site

- Unable to apply and control SNMES device or braces independently or with carer assistance.
- Other co-morbidities that could affect mobility/additional underlying condition e.g. stroke.

Cardiac pacemaker/history of cardiac problems will not be a reason for exclusion, but recruitment will be subject to cardiologist approval.

7.1.3 Nested qualitative studies (semi-structured interviews)

Inclusion criteria for people with MS

- People with MS who were eligible for and took part in either arm of the randomised controlled trial will be eligible for the nested qualitative study

Exclusion criteria for people with MS

- People with MS who were not eligible for and did not take part in either arm of the randomised controlled trial will be eligible for the nested qualitative study

Inclusion criteria for carers of people with MS who were involved in the study

- Carers or people who help look after people with MS that were involved in the study.
 - This includes provision of informal or formal care, assistance with activities related to the study including attendance of hospital visits, use of the SNMES device, recording of information related to healthcare visits, physical activity or exercise.

Exclusion criteria for carers of people with MS who were involved in the study

- Carers or people who help look after people with MS but were not involved in the study will not be eligible.

Inclusion criteria for healthcare practitioners and staff involved in the study

- Healthcare practitioners and staff (clinical and non-clinical) who were involved in the set up or delivery of the study.

Exclusion criteria for healthcare practitioners and staff involved in the study

- Healthcare practitioners and staff (clinical and non-clinical) who were not involved in the set up or delivery of the study.

7.2 RECRUITMENT

7.2.1 Screening

7.2.2 Recruitment for people with MS and the randomised controlled trial

Potential participants will be identified and screened by a researcher or a member of their care team via

- attendance at routine MS clinic appointments and
- searching of respective unit patient databases.

People with MS who meet the eligibility criteria will be provided with verbal and written information (study related documents and a Key Facts sheet).

They will be given as much time as they need to decide whether to take part and will have opportunities to ask questions. Participants who express an interest in the study will be followed up by their local research team or the research assistant (minimum 24 hours after being informed about the study) by telephone to discuss the study in more detail.

We will use purposive sampling across people with MS, people with MS and carer dyads to ensure diversity in characteristics of treatment allocation (intervention vs usual care), high versus low engagement/adherence with the SNMES intervention, study recruitment site and patient demographics/protected characteristics. We will also collect reasons for declining participation or stopping the intervention in the study (where possible). All people with MS in the study will be informed about the interview and consistent with the principles of purposive sampling be recruited based on personal and study characteristics.

People with MS and their carers will be recruited in dyads but interviewed separately.

7.2.3 Recruitment for carers of people with MS who were involved in the study

Carers of people with MS who were involved in the study will be recruited alongside recruitment of people with MS during

- attendance at routine MS clinic appointments
- during attendance at any of the hospital visits for the clinical measurements

Carers of people with MS will also be provided with verbal and written information (study related

documents and a Key Facts sheet). They will be given as much time as they need to decide whether to take part and will have opportunities to ask questions. Participants who express an interest in the study will be followed by their local research team or the research assistant (minimum 24 hours after being informed about the study) by telephone to discuss the study in more detail.

7.2.4 Recruitment for healthcare practitioners and staff involved in the study

Healthcare practitioners and staff involved in the study will be recruited from sites involved in the set-up, running and delivery of the study. Participants will be recruited during the processes related to site initiation, regular updates and study site close meetings. We will also use our regular study update newsletter to help with recruitment of healthcare practitioners and staff involved in the study.

Healthcare practitioners and staff who meet the eligibility criteria will be provided with verbal and written information. They will be given as much time as they need to decide whether to take part and will have opportunities to ask questions. Participants who express an interest in the study will be followed by a member of the Liverpool research team (minimum 24 hours after being informed about the study) by telephone to discuss the study in more detail.

7.3 INFORMED CONSENT

Three different consent forms have been developed. These are

- a combined consent form for people with MS in the randomised controlled trial and nested qualitative study
- a consent form for carers of people with MS who were involved in the randomised controlled trial
- a consent form for healthcare practitioners and staff involved in the study

Our PPI group has reviewed both the consent forms and accompanying information sheets to provide feedback on the overall readability, clarity and accessibility for people with MS. Based on their feedback we have made changes to the consent forms. This includes

- use of a single rather than multiple consent forms for people with MS in the randomised controlled trial and nested qualitative study.

- We have also received feedback regarding the information sheets and consent forms from our clinical partners.

Participants who express an interest in the study will be followed by their local research team or the research assistant (minimum 24 hours after being informed about the study) by telephone to discuss the study in more detail. A member of the research team will spend time discussing the research with participant and carer to ensure that all their questions and concerns are addressed.

Conversations during the consenting process have been identified as an important part of our recruitment and retention strategy. In combination with the information sheets and study materials, conversations at the consent stage will ensure that participants are fully informed of the study including:

- Time commitments, intervention and control group processes, are clear in relation to study duration
- Expectations of participants
- Understand importance of completing all relevant study outcomes / questionnaires and impact of drop out or non-engagement.

Consent will be obtained at the baseline measures visit for people with MS in the randomised controlled trial and nested qualitative study. During the visit, the participants and their carer will be provided with an additional opportunity to ask questions. Once that is completed, the researcher will provide the consent form to the participant and their carer and will explain the purpose of the appropriate consent form.

For carers of people with MS who were involved in the randomised controlled trial

Consent will be gained prior to the semi-structured interviews. Prior to the interview they will be provided with an additional opportunity to ask questions. Once that is completed, the researcher will provide the consent form to the participant and explain the purpose of the appropriate consent form.

For criteria for healthcare practitioners and staff involved in the study

Consent will be gained prior to the semi-structured interviews. Prior to the interview they will be

provided with an additional opportunity to ask questions. Once that is completed, the researcher will provide the consent form to the participant and explain the purpose of the appropriate consent form.

7.4 STUDY DESIGN AND METHODS OF DATA COLLECTION

7.4.1 Study design

A randomised controlled feasibility study comparing SNMES plus usual care versus usual care only with a nested qualitative study.

This will involve

- 1) A randomised controlled trial comparing SNMES plus usual care (n=25) versus usual care only (n=25). Total of 50 participants.
- 2) A nested qualitative study using semi-structured interviews for people with MS who took part in either arm of the randomised controlled trial and their carers (n=15-20).
- 3) A nested qualitative study using semi-structured interviews for healthcare practitioners and staff who were involved in the set up or delivery of the study and intervention (n=6-8).

7.4.2 Data collection

A study flowchart through has been provided under the heading “Study flowchart”. Participants will be required to attend the hospital a total of 3 times for the

- Baseline
- 3-month and
- 6-month timepoints. This is for clinical measures and collection of patients reported outcome measurements.

At each timepoint the relevant outcomes and clinical measures as identified in table 1 will be collected. Questionnaires may be sent out to participants (via email or post depending on their preference) prior to their attendance of the hospital visits. Instructions for collection of the

clinical measures and outcomes are outlined below.

An overview of the outcome measures to be collected and associated timepoints are provided below in table 1

Some participants and their carers will also have a qualitative interview after the 3-month or 6-month time points.

Table 1 – Overview of outcomes and timepoints for the study

Outcome	Description	Screening	Baseline	12 weeks*	6 months
Expanded Disability Status Scale (EDSS) ⁴⁴	Level of functional disability	✓		✓	✓
Demographic & disease characteristics	Patient information and disease classification		✓		
Timed up and Go (TUG) ^{45,46}	Muscle function / balance		✓	✓	✓
2 minute walk test (2MWT) ⁴⁷	Exercise tolerance		✓	✓	✓
Penn Spasm Frequency Scale (PSFS) ⁴⁸	Spasm frequency		✓	✓	✓
Multiple Sclerosis Impact Scale (MSIS-29v2) ⁸⁶	Quality of life measure		✓	✓	✓
Fatigue Severity scale (FSS) ⁴⁹⁺	Energy and drive (fatigue)		✓	✓	✓
5 -item Modified fatigue impact scale (MFIS-5) ⁺	Impact of fatigue on cognitive, physical and psychosocial function		✓	✓	✓
World Health Organisation Disability Assessment Schedule (WHODAS 2.0) ⁵⁰	Measure of disability		✓	✓	✓
EQ-5D-5L ⁵¹	Health related quality of life		✓	✓	✓
Resource use questionnaire (ModRUM) ^{52,53}	Health resources used and accessed			✓	✓
Numerical rating scale (Lower-limbs)	Pain		✓	✓	✓
MRC strength assessment (Lower-limbs)	Clinical scale of strength		✓	✓	✓
Joint range of movement (Lower-limbs)	Movement at the joints		✓	✓	✓
Modified Ashworth Scale ⁵⁴	Measure of muscle stiffness		✓	✓	✓
Level of impairment (Walking aids)	Type and number of		✓	✓	✓

	walking aids used				
--	-------------------	--	--	--	--

* (Primary endpoint); [†]measures of MS in exercise core set³⁴

7.4.3 Protocols for the completion of the clinical measures and outcome measures

7.4.4 Demographic and disease characteristics

7.4.4.1 Expanded disability status scale (EDSS)

The expanded disability subscale score is to be determined during screening, at 12 weeks and 6 months.

Grey shaded EDSS scores indicate eligibility criteria at baseline for involvement in study.

EDSS Score	Descriptor	Select
0	Normal neurological exam, no disability in any FS	
1.0	No disability, minimal signs in one FS	
1.5	No disability, minimal signs in more than one FS	
2.0	Minimal disability in one FS	
2.5	Mild disability in one FS or minimal disability in two FS	
3.0	Moderate disability in one FS, or mild disability in three or four FS. No impairment to walking	
3.5	Moderate disability in one FS and more than minimal disability in several others. No impairment to walking	
4.0	Significant disability but self-sufficient and up and about some 12 hours a day. Able to walk without aid or rest for 500m	
4.5	Significant disability but up and about much of the day, able to work a full day, may otherwise have some limitation of full activity or require minimal assistance. Able to walk without aid or rest for 300m	
5.0	Disability severe enough to impair full daily activities and ability to work a full day without special provisions. Able to walk without aid or rest for 200m	

5.5	Disability severe enough to preclude full daily activities. Able to walk without aid or rest for 100m	
6.0	Requires a walking aid – cane, crutch, etc. – to walk about 100m with or without resting	
6.5	Requires two walking aids – pair of canes, crutches, etc. – to walk about 20m without resting	
7.0	Unable to walk beyond approximately 5m even with aid. Essentially restricted to wheelchair; though wheels self in standard wheelchair and transfers alone. Up and about in wheelchair some 12 hours a day	
7.5	Unable to take more than a few steps. Restricted to wheelchair and may need aid in transferring. Can wheel self but cannot carry on in standard wheelchair for a full day and may require a motorised wheelchair	
8.0	Essentially restricted to bed or chair or pushed in wheelchair. May be out of bed itself much of the day. Retains many self-care functions. Generally has effective use of arms	
8.5	Essentially restricted to bed much of day. Has some effective use of arms retains some self-care functions	
9.0	Confined to bed. Can still communicate and eat	
9.5	Confined to bed and totally dependent. Unable to communicate effectively or eat/swallow	
10.0	Death due to MS	

7.4.4.2 Demographic characteristics

The following demographic characteristics will be recorded at baseline

- Date of birth
- Age at visit
- Sex assigned at birth
- Ethnicity
- Height
- Weight
- MS subtype
- Years since diagnosis
- Annual relapse rate^{1 55}
- Number of previous relapses

f

7.4.4.3 Relapses

A **relapse** is defined as “*a new symptoms or worsening of existing symptoms, causing neurological dysfunction for a minimum of 24 hours without any signs of infection or fever*”.⁵⁵ Exacerbation must be preceded by a stable 4-week period. In these cases, these will be noted by the study team. In the case of relapses, the study neurologist will be consulted and a time for return to the intervention will be agreed by them. Relapses will be confirmed in medical records and by a neurologist.

At each relevant time point e.g. follow up calls (Weeks 1 and 6), 12-weeks and 6-months post randomisation measurements, we will also ask and note if participants had any fluctuations in symptoms or medically confirmed relapses since enrolling on the study. We will additionally review the medical records of participants at the final follow up measure timepoint to identify if they have had any relapses.

¹ Annual relapse rate is calculated for each patient by dividing 365 days with the number of days in the study and multiplying by the number of relapses in the study period

7.4.4.4 Level of impairment (Walking aids)

Researcher to identify walking aids used

Walking aid	Tick
Independently mobile - no walking aids	
1 x walking stick (Fisher stick / cane)	
1 x elbow crutch	
2 x walking sticks (canes)	
2 x elbow crutches	
Rollator frame	
Zimmer frame	
Wheeled zimmer frame	
Ankle & foot orthosis (AFO) - single leg	
Ankle & foot orthosis (AFO) - bilaterally	
Functional electrical stimulation (FES) - single leg	
Functional electrical stimulation (FES) - bilaterally	
3 wheeled walker	
Gutter frame	
Gutter rollator frame	
Other (please state)	

7.4.5 Outcome measures related to MS symptoms and healthcare resource use

7.4.5.1 Multiple Sclerosis Impact Scale (MSIS- 29v2)

Based on Hobart et al 2001 ⁵⁶ and Hobart et al 2009 ⁸⁶

Self-reported questionnaire – see outcome measure sheet

7.4.5.2 Fatigue severity scale (FSS)

Based on Krupp et al 1989 ⁵⁷

Self-reported questionnaire – see outcome measure sheet

7.4.5.3 Modified Fatigue Impact Scale – 5-item version (MFIS-5)

Based on D'Souza et al 2016 ⁴⁹

Self-reported questionnaire – see outcome measure sheet

7.4.5.4 World Health Organization Disability Assessment Schedule 2.0 - 36 version (WHODAS 2.0)

Based on Young et al 2023 ⁵⁰

Self-reported questionnaire – see outcome measure sheet

7.4.5.5 European Quality of Life 5 Dimensions 5 Level Version (EQ-5D-5L)

Based on Balestroni et al 2012 ⁵¹

Self-reported questionnaire – see outcome measure sheet

7.4.5.6 Modular resource-use measure (ModRUM)

Key references Thorn et al 2018⁵², Garfield et al 2021⁵⁸, Garflied et al 2023⁵³

Self-reported questionnaire – see outcome measure sheet

7.4.5.7 Numerical rating scale (Lower limbs)

Based on The British Pain Society 2019⁵⁹

The Numerical Rating Scale (NPRS-11) is an 11-point scale for self-report of pain.

[figure not shown]
The respondent selects a whole number (integers 0–10) that best reflects the intensity (or other quality if requested of their leg pain.

- Legs scored together

Instructions for carrying out the test

The NPRS can be administered verbally (therefore also by telephone) or graphically for self-completion.

How intense was your pain on average last week (7 days) on a scale of 0 (no pain) to 10 (worst pain imaginable)

No pain

Worst pain imaginable

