7.4.5.8 Penn spasm frequency scale (PSFS)

Key references Priebe et al 1996⁶⁰ and Penn et al 1985⁶¹

Self-reported measure that assesses an individual's perception of spasticity frequency and severity.

- Legs scored together

Scoring: The Penn Spasm frequency Scale is comprised of two parts:

- Part 1 - spasm frequency and
- Part 2 - spasm severity.

Instructions for carrying out the test

Self-reported outcome measure. See outcome measure sheet for instructions and criteria.

A score is awarded based on the criteria below

Part 1 – Spasm frequency

Level	Description
0	No spasms
1	Mild spasms induced by stimulation
2	Infrequent full spasms occurring less than once per hour
3	Spasms occurring more than once per hour
4	Spasms occurring more than 10 times per hour

Part 2 – Spasm severity

Level	Description
1	Mild
2	Moderate
3	Severe

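### The printed pain question names no body part, although the outcome it feeds is leg pain with both legs scored together

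*Protocol*

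**What the plan says.** Table 1 in section 7.4.2 lists the measure as "Numerical rating scale (Lower-limbs", with pain as the construct, at baseline, 12 weeks and 6 months. The heading of section 7.4.5.7 repeats the restriction to the lower limbs. The text below it has the respondent choose the whole number "that best reflects the intensity (or other quality if requested of their leg pain", and a bullet adds "Legs scored together". Under the instructions for carrying out the test come a sentence on mode, "The NPRS can be administered verbally (therefore also by telephone) or graphically for self-completion", and then the question: "How intense was your pain on average last week (7 days) on a scale of 0 (no pain) to 10 (worst pain imaginable".

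Sections 7.4.5.1 to 7.4.5.6 and 7.4.5.8 refer the reader to an outcome measure sheet. Section 7.4.5.7 does not. Appendix 1 lists an outcome measure and clinical test pack, which is not part of the protocol text.

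The next item, the Penn spasm scale in section 7.4.5.8, is also self-reported. Level 1 of its frequency part reads "Mild spasms induced by stimulation", and that section defers: "Self-reported outcome measure. See outcome measure sheet for instructions and criteria".

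**The concern.** The definition and the question do not ask for the same thing. The heading, the table and the descriptive text all say leg pain; the sentence to be answered says pain. A respondent with painless legs and a sore back who takes the question at its word gives a non-zero score, and the database holds it as lower-limb pain.

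Section 5.1 lists selecting a primary outcome and determining the sample size for the definitive trial among the objectives, and section 9.2.1 describes the candidate outcome data as serving both. A pain score that mixes sites is a weaker basis for either. An intervention applied to the thigh and shank muscles would be judged partly on pain it was never meant to affect, and the mean and SD carried forward would describe an undefined mixture of leg and other pain.

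**Working it through.** No sample size, power or error rate is involved, and the protocol states no SD, expected difference or distribution for this score. The check is a comparison of texts.

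**1. What each place says about body site**

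| Place | Site named |
|---|---|
| Section 7.4.2, Table 1 | lower limbs |
| Section 7.4.5.7, heading | lower limbs |
| Section 7.4.5.7, description | leg pain |
| Section 7.4.5.7, scoring bullet | both legs, one score |
| Section 7.4.5.7, printed question | none |

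Four statements agree. The one the participant answers is the exception.

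**2. Does the respondent see the other four?** Not necessarily. The heading, description and bullet are written for staff. Voice, telephone and self-completion are all allowed, and section 7.4.2 lets questionnaires go out by email or post before a visit. With self-completion at home, nobody is present to add the missing words. If some staff add them and others do not, the construct can differ by site, visit or mode of completion.

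**3. Largest possible error for one respondent.** The scale runs from 0 to 10. With no leg pain and the worst imaginable pain elsewhere, the error is 10 − 0 = 10 points. This is a limit, not an expectation.

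**4. Average error.** The shift in an arm's mean is p × d, where p is the share answering about pain outside the legs and d is the mean difference between their recorded score and their true leg score. The protocol gives neither p nor d, so the product cannot be evaluated.

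**5. Effect on the SD.** Its direction is not determined. Adding pain from other sites can spread scores out, but it can also lift respondents with no leg pain towards the middle and narrow the spread.

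**6. Difference between arms.** The wording is the same for everyone, and section 7.4.7 randomises after all baseline measurements. Pain elsewhere is therefore expected to be balanced on average. The likely harm is a blurred measure rather than a systematic shift in favour of one arm.

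**The case against.** The strongest reply is that the sentence may not be the verbatim script. Where the protocol fixes spoken words, for the Timed Up and Go and the two-minute walk test, it introduces them as instructions to the participant; section 7.4.5.7 has no such label. A figure in that section is not reproduced, and the form participants complete may already mention the legs. This stands as a limit: the text shows that non-leg pain could be recorded, not that it will be. It does not remove the point. The question is printed under the instructions for the test, and this section, unlike its neighbours, refers to no sheet. If the sheet does say legs, the two documents differ and still need to be aligned.

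The consequence is also modest. The analysis in section 9.2.1 is descriptive, and the progression criteria are consent, retention and adherence, none of which uses this score.

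A reader might go further on the spasm scale. Because the trial device goes to one arm only ("A randomised controlled trial comparing SNMES plus usual care (n=25) versus usual care only (n=25"), level 1 could be taken to mean muscle activity caused by the device, biasing that arm alone. The documents support only a possible misreading. Section 7.4.5.8 hands instructions and criteria to a sheet that is not shown. Section 7.4.8 calls the effect of the device contractions, not spasms. Functional electrical stimulation is on the walking-aid checklist in section 7.4.4.4 for all participants, so electrical stimulation in general is not confined to one arm. Any numerical size for such a bias would rest on an invented share of participants.

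A reader might also infer that a participant whose spasms stop loses the best outcome, because the severity part starts at 1. That is not so: frequency level 0 records it.

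**Conclusion.** The point holds for the pain item as a mismatch between the defined outcome and the question printed to measure it. It is a real wording fault with a modest consequence: it weakens one candidate outcome among many and the estimates drawn from it, and leaves the progression decision untouched. The error for one respondent is bounded at 10 points; the average error is unknown, and no inflation of the SD can be claimed. The conclusion assumes that the printed sentence, or one like it, is what respondents receive. The unseen outcome measure sheet could show otherwise.

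The spasm wording is at most an optional clarification and not a demonstrated error.

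**What to change.** In section 7.4.5.7, replace the question with: *How intense was the pain in your legs (both legs together) on average over the last 7 days*, keeping the 0 to 10 scale and its anchors. Make the outcome measure sheet, and any telephone version, carry the same sentence. If scores have already been collected with the present wording, record which version each came from so that the two sets can be told apart.

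Optionally, add a note to the spasm scale sheet, identical in both arms, that stimulation in level 1 does not mean contractions produced by an electrical stimulation device while it is in use. The response levels stay as they are.

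The cost is one sentence in the protocol and on the sheet, plus one optional note, handled through the amendment route in section 10.1. There is no extra visit, item or burden for participants.
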